6.5 Secondary Efficacy Analyses

6.5.1 Hierarchical Testing

Primary inference for secondary efficacy endpoints will be based on analysis of the FAS analysis set or subsets of the FAS analysis set as defined below. Primary estimates and inference for time-to-event endpoints will be by Kaplan-Meier product-limit estimates and log-rank test (see Section 6.5.6 below). Primary estimates and inference for responder endpoints will be by logistic regression as described in Section 6.5.5 with missing data handled as indicated in Section 3.6. Primary estimates and inference for rate of change of continuous endpoints will be by a random-slopes linear mixed model (see Section 6.5.3 below). The sequence for testing secondary efficacy endpoints is the following:

1. Time to first decline of 2 points or greater post-baseline in the ALSFRS-R total score among participants in FAS with bulbar dysfunction at baseline defined as an ALSFRS-R bulbar domain (Q1-Q3) score of less than 12,

2. Proportion of participants experiencing no worsening in the ALSFRS-R bulbar domain (Q1-Q3) score from baseline through Week 24 among all participants in FAS,
3. Rate of change in respiratory function as measured by slow vital capacity (SVC) maximum percent predicted from baseline through Week 24 among participants in FAS with bulbar dysfunction at baseline defined as an ALSFRS-R bulbar domain (Q1-Q3) score of less than 12,
4. Time to first decline post baseline of 1 point or greater in the ALSFRS-R bulbar domain (Q1-Q3) score among all participants in FAS, and
5. Time to death or death equivalent through Week 24 among all participants in FAS.

If the primary analysis indicates a significant slowing in disease progression from the Bayesian shared-parameter, repeated-measures model of ALSFRS-R and mortality, then each secondary efficacy endpoint in succession would be declared significant in the specified sequence using a comparison-wise criterion of two-tailed $p < 0.05$. After the first failure to declare significance, no endpoints lower in the hierarchy can be significant. This sequential closed-testing procedure controls the overall type 1 error rate at 5%. Nominal comparison-wise p-values for secondary efficacy endpoints will also be reported.

All secondary efficacy analyses specified here for hierarchical testing will also be analyzed in the mITT analysis set as sensitivity analyses.

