6.5.7 CAFS

The primary CAFS analysis is as specified in the MPRDR. Additional, unadjusted CAFS analyses are the same as specified in the M-SAP, including specification that pair-wise comparison of change in ALSFRS-R total score for participants who cannot be ranked by time to death or death equivalent is to the maximum follow-up time at which both participants have an observation, and with the following additions:

1. HHD upper and lower extremity percentage and SVC will be analyzed by CAFS by substituting change from baseline for those secondary efficacy endpoints in place of ALSFRS-R total score,
2. An additional set of CAFS analyses will use multiple imputation to extend follow-up of ALSFRS-R total score, HHD upper and lower extremity percentage and SVC for participants who early terminate, withdraw consent, or are lost to follow-up,
3. An additional set of CAFS analyses will use time to death alone independent of any death equivalent,
4. An additional set of CAFS analyses for ALSFRS-R total score, HHD upper and lower extremity percentage, and SVC will adjust rank scores in a linear model with the

following covariates: time from ALS symptom onset, delta-FRS, baseline use of riluzole, and baseline use of edaravone, and

5. An additional set of CAFS analyses for ALSFRS-R total score, HHD upper and lower extremity percentage, and SVC will adjust rank scores in a linear model with the following covariates: time from ALS symptom onset, delta-FRS, baseline use of riluzole, baseline use of edaravone, and baseline serum NfL level.

The multiple imputation model used to extend follow-up of functional scores for participants who early terminate, withdraw consent, or are lost to follow-up will use linear regression with covariates of: time since symptom onset, delta-FRS, baseline riluzole use, baseline edaravone use, and each observed functional score prior to a missing assessment.

Inference from CAFS analyses is supportive of inference from the Bayesian shared-parameter, repeated-measures model for the primary outcome and supportive of inference from the random-slopes model for the secondary outcome of SVC. Primary inference from CAFS analyses will compare survival by time to death or death equivalent, will compare change in function to the last jointly observed time point, and will adjust for the specified covariates.

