6.5.10 Placebo Multiple Imputation

Placebo multiple imputation analyses are the same as specified in the M-SAP with the addition of baseline serum NfL level as a covariate and will be applied to the mixed model repeated-measures analysis of ALSFRS-R total score and the random-slopes analysis of SVC in the FAS analysis set.

The following SAS code specifies the imputation for an endpoint measured every 8 weeks:

```
proc mi data=work.outcomes seed=xxx nimpute=50 out=work.out_mi01
    minimum=. . . . . x x x x maximum=. . . . . y y y y minmaxiter=1000;
    class rlz edv trtrnd;
    fcs reg(Wk08 = sx2b1 dFRS rlz edv Wk00);
    fcs reg(Wk16 = sx2b1 dFRS rlz edv Wk00 Wk08);
    fcs reg(Wk24 = sx2b1 dFRS rlz edv Wk00 Wk08 Wk16);
    mnar model( Wk08 Wk16 Wk24 / modelobs=(trtrnd="0"));
    var sx2b1 dFRS rlz edv Wk00 Wk08 Wk16 Wk24;
run;
```

where Wk00, Wk08, Wk16, and Wk24 are the values of a given efficacy endpoint at the Baseline, Week 8, Week 16, and Week 24 Visits, respectively, trtrnd has a value of zero (0) for participants randomized to placebo, and x and y take appropriate values to specify the range of a given outcome measure (i.e., 0 and 48 for ALSFRS-R total score; 0 and . for HHD upper and lower extremity percentages and SVC).

Inference from these analyses is supportive of inference from the Bayesian shared-parameter, repeated-measures model for the primary endpoint and assess sensitivity to the missing data assumption of the random-slopes linear mixed model for SVC in the FAS analysis set. A separate analysis will include centered baseline serum NfL level as an additional covariate in both imputation stages.

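### Placebo multiple imputation for SVC is specified in the whole FAS, but the confirmatory SVC endpoint is tested only in participants with baseline bulbar dysfunction

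*SAP*

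**What the plan says.** **The tested endpoint.** SAP 4.1 and 6.5.1 list one SVC endpoint, third in the hierarchy: the rate of change in "slow vital capacity (SVC) maximum percent predicted from baseline through Week 24 among participants in FAS with bulbar dysfunction at baseline", where dysfunction means a bulbar domain score below 12. Sections 4.1 and 4.2 list no SVC endpoint for the whole FAS. Each step is judged at a "comparison-wise criterion of two-tailed" p below 0.05, in fixed sequence.

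**The model.** SAP 6.5.3 makes the random-slopes model primary for SVC. It gives the estimand population as the FAS and handles missing data under missing at random.

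**The missing-data check.** SAP 6.5.10 applies placebo multiple imputation to "the random-slopes analysis of SVC in the FAS analysis set". Its stated purpose for SVC is to "assess sensitivity to the missing data assumption of the random-slopes linear mixed model for SVC in the FAS analysis set".

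**Other support.** SAP 6.5.7 calls the CAFS analyses "supportive of inference from the random-slopes model for the secondary outcome of SVC" and names no analysis set. SAP 6.5.1 adds: "All secondary efficacy analyses specified here for hierarchical testing will also be analyzed in the mITT analysis set as sensitivity analyses". SAP 6.5.3 adds a supportive model with baseline serum NfL. For further sensitivity analyses of key secondary outcomes (6.5.11) and for missing data in continuous endpoints (3.6), the SAP refers to the Master SAP.

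**The concern.** A sensitivity analysis for missing data is useful when it changes the missing-data assumption and holds the rest of the estimand fixed. Here the population changes as well. If the whole-FAS imputation agreed with the primary SVC result, that would not show that the result in the bulbar subset is robust. If it disagreed, one could not tell whether the population or the assumption was responsible.

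What is at stake is the credibility of a multiplicity-controlled SVC claim. One can argue on clinical grounds that participants with bulbar dysfunction have more trouble with spirometry and more early deaths, so that missing at random is less plausible for them. That is an assumption: neither document gives missingness or mortality by bulbar status. The mismatch does not depend on it.

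**Working it through.** The plan gives no figure to reproduce, so the check sets the sections side by side.

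| SAP section | SVC analysis | Population stated | Missing-data assumption |
|---|---|---|---|
| 4.1, 6.5.1 | Key secondary 3 | FAS, baseline bulbar score below 12 | Missing at random, through 6.5.3 |
| 6.5.3 | Random-slopes estimand | FAS | Missing at random |
| 6.5.3 | Same model plus baseline NfL | None stated separately | Missing at random |
| 6.5.1 | Repeat of key secondary 3 | mITT | Missing at random |
| 6.5.10 | Placebo multiple imputation | FAS | Missing not at random (imputed from placebo) |
| 6.5.7 | CAFS on SVC | None stated | Deaths ranked; one variant uses multiple imputation |

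1. **Is FAS meant literally in 6.5.10?** The FAS is defined in 6.1, and 6.5.1 separates it from its parts: primary inference is "based on analysis of the FAS analysis set or subsets of the FAS analysis set as defined below". Section 6.5.10 uses the unqualified term for SVC twice. Read as written, it means the whole set.

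2. **Does another row relax missing at random in the tested subset?** The mITT set requires one dose and one post-baseline ALSFRS-R assessment, which changes who is included but not the model. The NfL model adds a covariate. Neither departs from missing at random. CAFS ranks deaths instead of treating them as missing, but no population is given for it.

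3. **Could the whole-FAS imputations be filtered to the subset afterwards?** Only in part. The code in 6.5.10 conditions on time since onset, delta-FRS, riluzole, edaravone and earlier SVC values, and the text adds NfL. It includes neither the baseline bulbar score nor site of onset. Missing values for bulbar participants would be drawn from a regression fitted to all placebo participants, with or without bulbar dysfunction.

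4. **How are the other steps treated?** For time-to-event endpoints based on scheduled assessments (steps 1 and 4), Section 3.6 attaches the 6.5.10 imputation as a sensitivity analysis. For responder endpoints (step 2), it attaches missing-not-at-random analyses from the Master SAP. Step 3 is the only assessment-based step whose missing-data check names a population other than its own.

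5. **How large is the mismatch?** The documents do not give the size of the bulbar subset. If a share *p* of the FAS has a baseline score below 12, then 1 − *p* of the participants in the planned check are outside the tested population. For an assumed *p* of 40% to 60%, that is 60% to 40%. This describes overlap only and says nothing about bias.

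6. **What does a subset imputation have to work with?** The protocol plans 40 placebo participants in this regimen. With the same assumed range, 40 × 0.40 = 16 to 40 × 0.60 = 24 would be in the subset. Shared placebo participants from regimens A, B and C add to this, in a number that the documents do not state.

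**The case against.** **The endpoint does have sensitivity analyses.** A reader might infer that key secondary 3 has none. The text does not support that: the mITT repeat covers it, and so does the NfL-adjusted model. What stands is narrower, namely that neither tests missing at random.

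**CAFS may already be in the right population.** A reader might also infer that the SVC CAFS is planned in the whole FAS. Section 6.5.7 does not say so. Because the only secondary SVC endpoint is the subset one, its wording can even be read as referring to that subset. The fair criticism is that the population is unstated.

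**FAS may be a template label.** Section 6.5.3 gives the FAS as population for the very model that tests the subset endpoint, so 6.5.10 may only mean FAS rather than mITT or per-protocol. This is the best argument on the other side. It makes the intent uncertain but does not supply the missing instruction, and Section 6.5.12 shows that SVC analyses in the full FAS are also planned. Protocol appendix Section 9.4 had SVC among all randomized participants, so the wording may have been carried over. That is an inference.

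**The Master SAP may fill the gap.** It was not available, so absence there cannot be asserted. A general rule in it for key secondary outcomes could cover step 3. However, the SAP ranks itself above the Master SAP where they differ, so its explicit FAS wording governs the analysis in 6.5.10.

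**The stakes are limited.** No sensitivity analysis gates the sequence. Steps 4 and 5 depend on the step 3 p-value only, and step 3 is reached only after the primary analysis and steps 1 and 2 succeed.

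**Conclusion.** The point holds in a limited form. The one missing-not-at-random analysis that the SAP sets out for the SVC random-slopes model is placed in the whole FAS, while the confirmatory SVC test is in the bulbar-dysfunction subset. Within the SAP, the missing-at-random assumption behind key secondary 3 is therefore not examined in the population tested. The unstated CAFS population and the FAS label in 6.5.3 add to the ambiguity.

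The primary analysis, the step 3 test and type I error control are unaffected. The effect on the SVC estimate cannot be sized, because the documents give no subset size, missingness rate or SVC variance. The conclusion rests on reading FAS in 6.5.10 as defined in 6.1, and on the SAP alone. It should be corrected because the check, as written, does not answer the question it is there to answer.

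**What to change.** - **6.5.10:** run the SVC placebo multiple imputation, both imputation and analysis stages, in FAS participants with a baseline bulbar domain score below 12, and name it as the sensitivity analysis for key secondary 3. Keep the whole-FAS run as additional.
- **6.5.7:** state the same subset for the SVC CAFS that supports key secondary 3.
- **6.5.3:** for key secondary 3, give the estimand population as that subset.

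The programming cost is a subset statement in existing code, and no new data are needed. The statistical cost is fewer placebo participants to fit the imputation model. Since Section 7.2 omits analyses that fail because of small samples, the pooled count in the subset should be checked before data lock.

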6.5.11 Additional Sensitivity Analyses of Primary and Key Secondary Outcomes

Sensitivity analyses of primary and key secondary efficacy outcomes are the same as specified in the M-SAP.

6.5.12 Subgroup Analyses

In addition to the subgroups specified in the M-SAP, the following additional subgroups will be analyzed in the random-slope model (see Section 6.5.3) for ALSFRS-R total score and SVC in the FAS analysis set:

- Baseline use of riluzole and edaravone (neither, riluzole only, edaravone only, both),
- Age (less than 65 years vs. 65 years or older),
- Sex (female vs. male),
- Race (white vs. any minority race with greater than 5% prevalence in the sample),
- Ethnicity (Hispanic or Latino vs. non-Hispanic or Latino),
- Weight (less than 43 kg, 43 to less than 56 kg, 56 to less than 77 kg, 77 to less than 150 kg, 150 kg or more),

- BMI (less than 18.5 kg/m², 18.5 to less than 25 kg/m², 25 to less than 30 kg/m², 30 to less than 40 kg/m², 40 kg/m² or more),
- Chronic kidney disease (CKD) stage (stage 1 or better [eGFR 90 mL/min/1.73m² or more], stage 2 [eGFR 60 to 89 mL/min/1.73m²], stage 3 [eGFR 30 to 59 mL/min/1.73m²], stage 4 [eGFR 15 to 29 mL/min/1.73m²], stage 5 [eGFR less than 15 mL/min/1.73m²]),
- Time since onset of weakness (less than 18 months vs. 18 months or longer),
- El Escorial and time since onset of weakness (El Escorial definite and less than 18 months vs. not both),
- Baseline symptom severity (all ALSFRS-R questions scored 2 or greater vs. any question scored 0 or 1),
- Early disease state (all ALSFRS-R questions scored 2 or greater, SVC 80%-predicted or greater, and time since symptom onset less than 24 months vs. not meeting all three criteria),
- Baseline serum urate concentration (less than 5.5 mg/dL vs. 5.5 mg/dL or greater),
- Baseline plasma NfL concentration (by median split), and
- Site (individual sites with at least 5 participants per treatment group and all participants from sites with fewer than 5 participants per treatment group pooled).

For each classification, unknown, not reported, and missing will be considered one group. All individuals not included in a specified subgroup will be combined into a mixed, "other" group. The "other" group will be included in analyses if its prevalence is greater than 5%; otherwise, the "other" group will be excluded.

6.5.13 Comparison of Controls across Regimens

Comparisons of placebo participants across regimens are the same as specified in the M-SAP with separate analyses that include baseline serum NfL level as an additional covariate in adjusted analyses plus applicable interaction terms as relevant to a given model.

6.5.14 Pharmacokinetic Analyses of Pridopidine

Plasma concentrations of pridopidine will be summarized by treatment group and visit in the ERO sample. Concentrations below the limit of quantitation (BLQ) will be replaced with one half of the lower limit of quantitation. Summaries will include number of observations, number and percentage with concentrations BLQ, arithmetic mean, median, standard deviation, minimum, maximum, geometric mean, geometric coefficient of variation (calculated as $\sqrt{\exp(\text{variance of log-transformed concentrations}) - 1}$), and 95% confidence bounds for the geometric mean assuming log-normally distributed data.

Plasma concentration data of pridopidine may be subjected to population pharmacokinetic analysis to derive population estimates of pharmacokinetic parameters and test the effect of various covariates such as age, weight, and sex. Details of the analysis will be described in a separate data analysis plan (DAP). This analysis may be performed by combining data from the current study with data from other studies of pridopidine, if deemed appropriate. The population pharmacokinetic analysis will be performed by Prilenia and reported in a separate modelling report.

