Participants who complete the full study regimen (24 weeks) will have the option to enroll into the OLE period of the study and receive pridopidine 45 mg orally BID (total daily dose of 90 mg), following a 2 week up-titration period at QD.

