6.1.8 Week 24 Visit or Early Termination Visit

Participants Not Enrolling into the OLE

Only a pre-dose ECG is required at this visit for participant who are not enrolling into the OLE.

If a participant's visit occurs in the morning, the participant should be instructed not to take the morning dose at home, and the morning dose should be administered in-clinic after the pre-dose ECG. If a participant's visit occurs in the afternoon, the participant should be instructed to take the morning dose immediately upon waking in the morning, and the second dose should be taken after the pre-dose ECG.

Participants Enrolling into the OLE

A pre-dose and post-dose ECG are required for participants who enroll into the OLE. The SI should confirm the mean QTcF following the pre-dose triplicate ECG. If the mean QTcF is >450 ms for men and >470 ms for women, then participant will not be eligible to continue into the OLE.

If a participant's visit occurs in the morning, the participant should be instructed not to take the morning dose at home. A pre-dose triplicate ECG should be collected prior to administration of the first dose of OLE IP in-clinic. A single post-dose ECG should then be collected 1-2 hours after administration of the first dose of OLE IP.

If a participant's visit occurs in the afternoon, the participant should be instructed to take the morning dose immediately upon waking in the morning, and a pre-dose triplicate ECG should be collected prior to administration of the first dose of OLE IP in-clinic (which will be the 2nd daily dose).

A single post-dose ECG should then be collected 1-2 hours after administration of the first dose of OLE IP.

This visit will take place on Day 168 ± 7. The following procedures will be performed at either the Week 24 Visit or the Early Termination Visit:

- Home Spirometry
- ALSAQ-40
- CNS-BFS
- CNS-LS
- **Triplicate** ECG monitoring **BEFORE** IP administration
- Administer **single** ECG 1-2 hours **AFTER** IP is administered (only for participants enrolling into the OLE)
 - Note: if the participant is taking Nuedexta, the Nuedexta dose should be taken within 6 hours prior to the pre-dose ECG. If participant has taken Nuedexta outside of this window, the ECG should still be completed and a protocol deviation recorded. Refer to the MOP for additional guidance.
- Plasma PK collection
 - **after** the pre-dose ECG for participants NOT participating in the OLE

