 - **after** the post-dose ECG for participants participating in the OLE
 - All blood samples should be collected after the ECG is performed. If the blood samples cannot be collected after the ECG due to scheduling constraints, blood samples should be collected at least one hour prior to the ECG.
- Voice Recording
- Uninstall Smartphone App
- Dispense IP [See note below.]
- Remind participant to bring investigational product to the next visit (only if continuing in OLE)

Note: Drug is only dispensed at this visit if the participant is continuing in the OLE.

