6.1.10 Process for Early Terminations

A research participant may choose to discontinue their participation at any time for any reason. The SI or designee will encourage the participant to follow the study protocol under intent-to-treat principle and follow the study visits, off treatment, up to the week 24 visit. If a participant decides to discontinue IP, but will complete the protocol, an in-person Early Termination Visit and Follow-Up Safety Call is not necessary.

Participants who early terminate from the study and do not complete the protocol will be asked to be seen for an in-person Early Termination Visit and complete a Follow-Up Safety Call. If a participant is not able to be seen in-person, safety assessments and others that can be conducted remotely should be performed.

The in-person Early Termination Visit should be scheduled as soon as possible after a participant early terminates. If the participant early terminates during the placebo-controlled portion of the Regimen, all assessments that are collected at the Week 24 in-clinic visit should be conducted. If the participant early terminates during the OLE period, all assessments that are intended for collection at the OLE Week 24 in-clinic visit should be conducted. The Follow-Up Safety Call should be completed approximately 28 days after the last dose of IP.

If the Early Termination Visit occurs approximately 28 ± 3 days after the last dose of IP, the information for the Follow-Up Safety Call can be collected during the Early Termination Visit, and a separate Follow-Up Safety Call does not need to be completed. If the in-person Early Termination Visit does not occur within 28 ± 3 days of the last dose of IP, the Follow-Up Safety Call should occur approximately 28 ± 3 days after the last dose of IP and the Early Termination Visit will be completed after the Follow-Up Safety Call.

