6.2 Open Label Extension

Participants who completed the placebo-controlled portion of the trial on drug, will be eligible to continue in the OLE as outlined in the SOA. Participants will first be asked about their desire to continue in the OLE at the Regimen-Specific Screening Visit. They will also be asked to *re-confirm* whether they want to continue in the OLE at the Week 16 Visit of the placebo-controlled period. In the OLE, pridopidine will be provided by Prilenia Therapeutics, until the primary results of the 24 week double-blind portion of the study are available, or they terminate development of pridopidine for ALS.

To preserve the blind, all participants in the OLE, regardless of whether they were in the active or placebo arm of the study initially will need to initiate the OLE at a QD dose and then up-titrate to BID after 2 weeks.

Modifications to OLE Schedule

Designated visits in the Schedule of Activities for the OLE (i.e. Week 8, Week 16) may be conducted via telemedicine (or phone if telemedicine is not available) with remote services

instead of in-person if needed to protect the safety of the participant due to a pandemic or other reason. If a planned in-clinic visit is conducted via telemedicine (or phone if telemedicine is not available) with remote services, only selected procedures will be performed. Instructions on how to document missed procedures are included in the MOP.

In addition to the procedures in the Master Protocol that should be conducted during the phone or telemedicine and remote visits, the following regimen-specific procedures should be completed:

- Home Spirometry
- CNS-BFS
- CNS-LS
- ALSAQ-40

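### Unless the M-SAP excludes them, Week 24 PK samples drawn after the first open-label pridopidine dose enter the placebo row of the PK summary, and the active row may mix sampling times

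*SAP*

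**What the plan says.** **Analysis.** SAP 5.13 has the Week 4 and Week 24 plasma samples assayed for pridopidine. SAP 6.5.14 then says: "Plasma concentrations of pridopidine will be summarized by treatment group and visit in the ERO sample". The listed statistics include the number and percentage below the limit of quantitation (BLQ), arithmetic and geometric means, geometric CV and 95% bounds for the geometric mean. BLQ values are set to half the lower limit. Nothing separates samples by OLE entry, by time since dose or by whether the participant is still on drug. SAP 6.1 leaves the ERO definition to the M-SAP.

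**Sampling.** Protocol 6.1.8 sets two Week 24 PK times:
- OLE entrants are sampled after "the post-dose ECG for participants participating in the OLE". On the dose before that ECG, the same section says: "A single post-dose ECG should then be collected 1-2 hours after administration of the first dose of OLE IP".
- Everyone else is sampled after "the pre-dose ECG for participants NOT participating in the OLE".

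If scheduling prevents a draw after the ECG, "blood samples should be collected at least one hour prior to the ECG".

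**OLE entry.** Protocol 6.2 gives pridopidine to OLE entrants from both arms, starting once daily. Protocol 3 says completers "will have the option to enroll into the OLE period of the study and receive pridopidine 45 mg orally BID". Protocol 6.2 is narrower: "Participants who completed the placebo-controlled portion of the trial on drug, will be eligible to continue in the OLE". Under Protocol 6.1.10, participants who stop study drug are encouraged to "follow the study visits, off treatment, up to the week 24 visit".

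**The concern.** The summary is organised by randomised group and visit, while the sampling time at one of its two visits depends on OLE entry. A placebo participant who enters the OLE is, by default, sampled soon after a first active dose. Filed under placebo at Week 24, that concentration reads as exposure during the double-blind period, which it is not. The BLQ percentage would show that something is odd, but it would not repair the mean, geometric mean, CV or bounds in the same row.

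The active arm raises a separate and weaker question: whether its Week 24 values were taken at comparable times after dosing. What is at stake is the readability of one exploratory table, and of any description of exposure drawn from it.

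**Working it through.** The documents give no figure for this summary, so there is nothing to reproduce. The check is a chain of text followed by illustrative arithmetic.

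**1. Order of events at Week 24 for an OLE entrant.** Put the OLE dose at time 0. The post-dose ECG falls at 1-2 h and the default PK draw follows it. The fallback draw is at least 1 h before the ECG, so no later than 0 h if the ECG is at 1 h, and no later than 1 h if it is at 2 h. It can therefore fall on either side of the dose. The default draw is always after it.

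**2. How many placebo samples.** Planned allocation is 120 active and 40 placebo (Protocol, RSA Summary). Assumptions: 70-90% still on drug at Week 24, and 50-90% of those entering.
- Entry fraction: 0.7 × 0.5 = 0.35 to 0.9 × 0.9 = 0.81.
- Placebo entrants: 40 × 0.35 = 14 to 40 × 0.81 = 32.4.
- Active entrants: 120 × 0.35 = 42 to 120 × 0.81 = 97.2.
- Non-entrants: 40 − 32.4 = 7.6 to 40 − 14 = 26 placebo; 120 − 97.2 = 22.8 to 120 − 42 = 78 active.
- Off drug, active: 120 × 0.1 = 12 to 120 × 0.3 = 36.

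Entrant counts are upper limits, because fallback draws may precede the dose. All counts fall further with deaths and missed visits.

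**3. Level in a placebo entrant.** Protocol inputs: half-life about 10 h at steady state, median Tmax 1.25-2 h, mean peak 618 ng/mL at 45 mg BID, doses 7-10 h apart. The protocol's model has two compartments, with parameters not given; a one-compartment model is used here for scale only.
- *Instant absorption.* The steady-state afternoon peak, in units of one dose, is (1 + 0.5^(g/10)) / (1 − 0.5^(24/10)) for a dose gap of g hours. For g = 7 this is 1.616 × 1.234 = 1.993, so one dose gives 618 / 1.993 = 310 ng/mL. For g = 10 it is 1.5 × 1.234 = 1.851, giving 334 ng/mL.
- *Gradual absorption.* With assumed absorption rate 1.0-2.5 per h, sampling 1.25-2.25 h after dosing and first-dose half-life 5-10 h, the ratio of one dose to the steady-state peak is about 0.37-0.53, or roughly 230-330 ng/mL.

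**4. Effect on the placebo row.** Suppose half of 40 placebo samples are at 280 ng/mL and half are BLQ, with an assumed lower limit of 1-5 ng/mL, so BLQ values become 0.5-2.5.
- Geometric mean: √(0.5 × 280) = 11.8 to √(2.5 × 280) = 26.5 ng/mL.
- Geometric CV at the 5 ng/mL limit: the log values lie ± ln(280/2.5)/2 = ± 2.36 from their mean, so the variance is about 5.57 and √(e^5.57 − 1) is about 16, or above 1,600%. It is larger at the 1 ng/mL limit.

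No participant in the row has a concentration near that geometric mean.

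**5. Active arm.** A BID participant entering the OLE takes the same 45 mg capsule. Protocol 6.1.3 also places the default Week 4 draw after a 1-2 h post-dose ECG. Entrants' Week 4 and Week 24 samples therefore share default timing.

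Non-entrants differ. Protocol 6.1.8 puts both their in-clinic dose and their PK draw after the pre-dose ECG, without saying which comes first. If the draw comes first:
- Gradual absorption: pre-dose/post-dose ratio 0.43-0.55 (morning) and 0.51-0.64 (afternoon), that is 36-57% lower.
- Instant absorption: ratio to peak 0.38-0.41 (morning) and 0.46-0.50 (afternoon), that is 50-62% lower.
- Off drug for 72 h: 0.5^(72/10) = 0.7% of the earlier level.

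If the dose comes first, the pre-dose/post-dose difference need not arise.

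**The case against.** **The M-SAP may already deal with this.** This is the strongest objection, and it stands as a condition. SAP 1 describes the R-SAP as modifications to the M-SAP for the placebo-controlled period, and the ERO definition sits in the M-SAP. The scope statement alone does not clearly settle it: Week 24 is a placebo-controlled-period visit, and nothing supplied says whether the period ends at the first OLE dose or with the visit.

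**The result is visible and untested.** The BLQ percentage would expose the placebo anomaly, no hypothesis is tested, and 6.5.14 provides for possible population PK under a separate plan. This limits the severity. It does not make the placebo row correct.

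Some stronger readings are tempting but not supported:
- *The OLE dose contaminates the active row.* A BID participant receives the same capsule strength at the same default sampling time as at Week 4.
- *Non-entrants are trough samples, so the active row must mix times.* The order of draw and dose is not stated, so it may mix them.
- *The TEAE cut-off in SAP 6.6.1 is a model that the PK section left out.* That boundary is an inclusive date. The first OLE dose and the PK draw fall on the same visit day, so the rule would exclude none of these samples.
- *A planned Week 4 to Week 24 contrast is invalid.* SAP 4.2 lists change in plasma concentration as an endpoint, but 6.5.14 specifies visit summaries only, with no reference visit or method for change.
- *All off-drug participants are non-entrants.* Protocol 6.2 implies this, but Protocol 3 offers the OLE to completers without an on-drug condition.

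**Conclusion.** The point holds, conditionally and at minor severity. On the documents supplied, the stated rule would place open-label pridopidine levels in the Week 24 placebo row, and that row's mean, geometric mean and confidence bounds would not describe double-blind exposure. The condition is that the M-SAP contains no exclusion of samples taken after the first OLE dose.

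The number affected depends on OLE uptake, which is not stated; 14-32 of 40 placebo participants is an illustration under assumed retention and entry. The 230-330 ng/mL level rests on a one-compartment approximation with assumed absorption and first-dose half-life.

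For the active arm the conclusion is weaker: its Week 24 row may combine different dose-relative times and off-drug participants. No firm bound on the pooled shift can be given, because it depends on uptake, on the unstated order of draw and dose in non-entrants, and on how many are off drug. The output is exploratory and descriptive, and primary efficacy is unaffected.

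**What to change.** In SAP 6.5.14, unless the M-SAP already does so:
1. Flag each Week 24 sample as before or after the first OLE dose, from recorded dose and sample times.
2. Report placebo-arm samples taken after the OLE dose separately from the double-blind placebo summary.
3. Keep all active-arm samples, but show them by pre-dose or post-dose status, with off-drug participants identified.
4. If a change from Week 4 is reported, base it on samples at the same dose-relative time.

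If the M-SAP already excludes post-OLE-dose samples, a cross-reference in 6.5.14 is enough for the placebo row.

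The cost is SAP wording and one derived flag, and it relies on dose and sample times having been recorded. The downside is smaller Week 24 cells. Under the assumptions above, about 8-26 placebo samples remain in the double-blind summary, plus any entrants drawn before the OLE dose. Active samples divide into up to about 42-97 from entrants and 23-78 from non-entrants, less deaths and missed visits. No sample is discarded.
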